8.2.1. Physical Examinations

A complete physical examination (including height [at screening only], body weight, skin examination, and other body systems) will be performed at screening, Week 24, and Week 48. A symptom-directed physical examination (including body weight) will be performed at the time points indicated in the Schedule of Activities.

A complete physical examination includes the following: general appearance, eyes, ears, nose, throat, cardiovascular system, respiratory system, gastro-intestinal system, and skin and mucous membranes. A neurological and musculoskeletal examination will be performed, as well as an examination of the lymph nodes. Body weight and temperature will be measured. Height will be measured at the screening visit only.

8.2.2. Vital Signs

Temperature, pulse rate, and supine SBP and DBP will be assessed at the time points indicated in the Schedule of Activities.

Blood pressure and pulse rate measurements will be assessed with a completely automated device. All values will preferably be registered on a built-in recorder so that measurements are observer independent. Manual techniques will be used only if an automated device is not available.

Blood pressure and pulse rate measurements should be preceded by at least 5 minutes of rest in a quiet setting without distractions (eg, television, cell phones).

Clinically relevant abnormalities in vital signs are defined in Section 10.7, Appendix 7, Cardiovascular Safety Abnormalities.

8.2.3. Electrocardiograms

Twelve-lead triplicate ECGs will be collected at the time points indicated in the Schedule of Activities and when clinically indicated.

During the collection of ECGs, participants should be in a quiet setting without distractions (eg, television, cell phones). Participants should rest in a supine position for at least 5 minutes before ECG collection and should refrain from talking or moving arms or legs.

At each time point at which triplicate ECGs are required, 3 individual ECG tracings should be obtained as closely as possible in succession, but no more than 2 minutes apart. The full set of triplicates should be completed in less than 10 minutes.

Evaluation of the triplicate 12-lead ECGs will be based on the mean value of the triplicate parameters.

All ECGs will be read centrally. Preferably, all ECGs will be read and interpreted under supervision of one and the same qualified person. Day 1, pre-dose ECG assessment will also be done locally on-site to determine eligibility.

Clinically relevant abnormalities in ECG are defined in Section 10.7, Appendix 7, Cardiovascular Safety Abnormalities.

8.2.4. Clinical Safety Laboratory Assessments

Blood samples for serum chemistry, hematology, and coagulation, and a urine sample for urinalysis, urine chemistry, and renal biomarkers will be collected as noted in Section 10.2, Appendix 2, Clinical Laboratory Tests. The investigator must review the laboratory results, document this review, and record any clinically relevant changes occurring during the study in the AE section of the CRF. The laboratory reports must be filed with the source documents.

Participants need to have fasted for at least 10 hours before biochemistry samples are taken for measurement of phosphate, calcium, creatinine, and lipids. Participants are to bring their oral study intervention with them to each study visit and have that day's intake at the site.

If a grade 3 or grade 4 laboratory abnormality occurs, that is considered to be clinically significant by the investigator, a confirmatory test must be performed preferably within 48 hours but no later than 72 hours after the results have become available.

For this study, the laboratory abnormality of cholesterol increase is identified as laboratory abnormality of interest.

8.3. Adverse Events and Serious Adverse Events

Timely, accurate, and complete reporting and analysis of safety information from clinical studies are crucial for the protection of participants, investigators, and the sponsor, and are mandated by regulatory agencies worldwide. The sponsor has established Standard Operating Procedures in conformity with regulatory requirements worldwide to ensure appropriate reporting of safety information; all clinical studies conducted by the sponsor or its affiliates will be conducted in accordance with those procedures.

Adverse events will be reported by the participant (or, when appropriate, by a caregiver, surrogate) for the duration of the study.

For further details on AEs and SAEs (Definitions and Classifications; Attribution Definitions; Severity Criteria; Special Reporting Situations; Procedures) as well as product quality complaints, refer to Section 10.4, Appendix 4, Adverse Events: Definitions and Procedures for Recording, Evaluating, Follow-Up, and Reporting.

8.3.1. Time Period and Frequency for Collecting Adverse Event and Serious Adverse Event Information

All Adverse Events

All AEs and special reporting situations, whether serious or non-serious, will be reported from the time a signed and dated ICF is obtained until completion of the participant's last study-related procedure, which may include contact for follow-up of safety. Serious AEs, including those spontaneously reported to the investigator within 30 days after the last dose of study intervention, must be reported using the SAE Form. The sponsor will evaluate any safety information that is spontaneously reported by an investigator beyond the time frame specified in the protocol.

Serious Adverse Events

All SAEs occurring during the study must be reported to the appropriate sponsor contact person by study-site personnel within 24 hours of their knowledge of the event.

Information regarding SAEs will be transmitted to the sponsor using the SAE Form, which must be completed and signed by a physician from the study site, and transmitted to the sponsor within 24 hours. The initial and follow-up reports of an SAE should be made by facsimile (fax).

8.3.2. Method of Detecting Adverse Events and Serious Adverse Events

Care will be taken not to introduce bias when detecting AEs or SAEs. Open-ended and nonleading verbal questioning of the participant is the preferred method to inquire about AE occurrence.

Solicited Adverse Events

Solicited AEs are predefined local (at the injection site) and systemic events for which the participant is specifically questioned.

Unsolicited Adverse Events

Unsolicited AEs are all AEs for which the participant is not specifically questioned.

8.3.3. Follow-up of Adverse Events and Serious Adverse Events

AEs, including pregnancy, will be followed by the investigator as specified in Section 10.4, Appendix 4, Adverse Events: Definitions and Procedures for Recording, Evaluating, Follow-up, and Reporting.

8.3.4. Regulatory Reporting Requirements for Serious Adverse Events

The sponsor assumes responsibility for appropriate reporting of AEs to the regulatory authorities. The sponsor will also report to the investigator (and the head of the investigational institute where required) all suspected unexpected serious adverse reactions (SUSARs). The investigator (or sponsor where required) must report SUSARs to the appropriate Independent Ethics Committee/Institutional Review Board (IEC/IRB) that approved the protocol unless otherwise required and documented by the IEC/IRB. A SUSAR will be reported to regulatory authorities unblinded. Participating investigators and IEC/IRB will receive a blinded SUSAR summary, unless otherwise specified.

8.3.5. Pregnancy

All initial reports of pregnancy in female participants or partners of male participants must be reported to the sponsor by the study-site personnel within 24 hours of their knowledge of the event using the appropriate pregnancy notification form. Abnormal pregnancy outcomes (eg, spontaneous abortion, fetal death, stillbirth, congenital anomalies, ectopic pregnancy) are considered SAEs and must be reported using the SAE Form. Any participant who becomes pregnant during the study must discontinue further investigational intervention.

Follow-up information regarding the outcome of the pregnancy and any postnatal sequelae in the infant will be required.

8.3.6. Specific Toxicities

For participants reporting ALT/AST elevations, rash, ISRs, acute systemic allergic reactions, and renal complications as specified in the DAIDS Toxicity Grading Scale (see Section 10.9, Appendix 9, DAIDS Table), the following should be done.

8.3.6.1. Intervention-emergent ALT/AST Elevations

Elevated liver enzyme activity can be triggered by the underlying HBV disease as well as by the study intervention.

Management of intervention-emergent ALT/AST elevations is presented graphically in Section 10.6, Appendix 6: Intervention-emergent ALT/AST Elevations, and is described below.

Any intervention-emergent elevation of ALT and/or AST $\ge 3x$ ULN and $\ge 3x$ nadir (ie, lowest value during study participation) should trigger an assessment of confounding factors (alcohol intake, change in concomitant medication, and comorbidities) and should trigger a confirmatory

study visit to repeat laboratory testing of AFP, ALT, AST, ALP, bilirubin (total and direct), INR, albumin, and HBV DNA. Additional tests should be considered based on clinical judgement (refer to Section 10.6, Appendix 6: Intervention-emergent ALT/AST Elevations). The confirmatory visit should be scheduled as soon as possible, preferably within 7 days of the receipt of the initial ALT/AST results. In case the repeat laboratory testing shows an isolated ALT/AST elevation (ie, with stable albumin, bilirubin [total and direct], and INR) the participant may continue study intervention. In case of confirmed ALT elevation >1,000 U/L and >3x the baseline value, investigational intervention should be discontinued. In both cases, NA treatment should be continued. The participant will be monitored (laboratory testing of ALT, AST, ALP, bilirubin [total and direct], INR, albumin, and HBV DNA) on a weekly basis until ALT and/or AST levels have returned to 50% of the maximal value.

If the ALT and/or AST level is $\ge 3x$ ULN and $\ge 3x$ nadir and is associated with any of the following laboratory results or clinical symptoms:

- INR \geq 1.5, OR
- direct bilirubin >1.5x ULN, OR
- serum albumin <3.0 g/dL, OR
- ascites, hepatic encephalopathy, or liver-related symptoms (eg, severe fatigue, nausea, vomiting, right upper quadrant pain in the absence of an alternative medical explanation), OR
- other indication of reduced liver function

the participant should discontinue investigational intervention and should be monitored on a weekly basis or as per good clinical practice until ALT and/or AST levels have returned to 50% of the maximal value and, if present, liver-related symptoms have improved. NA treatment should be continued. Additional tests can be considered based on clinical judgement.

The NA re-treatment criteria during follow-up are presented in Section 6.7.

8.3.6.2. Rash

Participants should be informed that they should contact their doctor immediately when they notice any generalized skin reaction. This skin reaction should be evaluated in the clinic the same day (if possible) or the next day.

All rash events should be captured in the AE section of the CRF. A separate Rash page will be completed in case of a rash event.

Monitoring of the evolution of rash events will be performed as described in Table 9 in Section 10.5, Appendix 5, Rash Management.

When safety blood samples are drawn as per the rash management guidelines, these should be processed by the local laboratory. The following parameters will need to be tested: AST, ALT, sedimentation rate, complete blood cell count (including hemoglobin, hematocrit, red blood cell

[RBC] count, white blood cell [WBC] count, differential count [neutrophils, lymphocytes, monocytes, eosinophils, and basophils], and platelet count), and creatinine. The values of the local laboratory assessments need to be transcribed in the CRF by the study site personnel.

The participant may be treated symptomatically until the rash resolves. Oral antihistamines (eg, cetirizine, levocetirizine) and/or topical corticosteroids may provide symptomatic relief but effectiveness of these measures has not been established. If systemic corticosteroids exceeding 5 mg of prednisolone equivalent/day are required for treatment of rash, the study intervention needs to be permanently discontinued. If the rash is considered to be most likely due to concomitant illness or non-study drugs, standard management, including discontinuation of the likely causative agent, should be undertaken.

Injection Site Reactions

At the time points specified in the Schedule of Activities or at an unscheduled visit if needed, an evaluation of the injection site will be performed based on participant's description and/or physical examination. Evaluation will include at a minimum the time of occurrence, time of resolution and a description of the abnormality including its maximal diameter. For each ISR, information on pain, erythema, induration and pruritus should be obtained as specified in the DAIDS scale (see Section 10.9, Appendix 9, DAIDS Table).

All ISRs (including ISRs below grade 1) will need to be recorded in the special events section of the CRF.

Digital pictures will be taken when considered appropriate; all efforts should be made to collect images in case of grade 3 and 4 ISRs. Digital pictures will only be taken and collected from participants who consent separately to this component of the study. If digital pictures are required, they should be de-identified and provided to the sponsor.

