1. PROTOCOL SUMMARY

1.1. Synopsis

A Phase 2b, Multicenter, Double-blind, Active-controlled, Randomized Study to Investigate the Efficacy and Safety of Different Combination Regimens Including JNJ-73763989 and/or JNJ-56136379 for the Treatment of Chronic Hepatitis B Virus Infection

JNJ-73763989 (JNJ-3989) is a liver-targeted antiviral therapeutic for subcutaneous injection designed to treat chronic hepatitis B virus (HBV) infection via a ribonucleic acid interference (RNAi) mechanism. Engagement of the cellular RNAi machinery by JNJ-3989 results in specific cleavage of HBV ribonucleic acid (RNA) transcripts, thereby reducing the levels of HBV proteins and the pre-genomic ribonucleic acid (pgRNA), the precursor of viral relaxed circular deoxyribonucleic acid (DNA). The RNAi triggers in JNJ-3989 injection are designed to target all HBV RNA transcripts derived from covalently closed circular DNA (cccDNA), as well as transcripts derived from integrated viral DNA. The latter has been suggested to be a significant source of hepatitis B surface antigen (HBsAg) in hepatitis B e antigen (HBeAg)-negative patients or patients on long-term treatment with nucleos(t)ide analogs (NAs), the current standard of care.

JNJ-56136379 (JNJ-6379) is an orally administered capsid assembly modulator that is being developed for the treatment of chronic HBV infection. JNJ-6379 binds to hepatitis B core protein and interferes with the viral capsid assembly process, thereby preventing the polymerase-bound pgRNA encapsidation. This results in the formation of HBV capsids, devoid of HBV DNA or RNA (non-functional capsids), and ultimately in the inhibition of HBV replication. In addition, JNJ-6379 also acts at an early stage of the viral life cycle by inhibiting the de-novo formation of cccDNA potentially by interfering with the capsid disassembly process.

Study intervention refers to JNJ-3989 or placebo, JNJ-6379 or placebo, and NA.

OBJECTIVES AND ENDPOINTS

The primary and secondary objectives and endpoints of this study are listed below.

Objectives	Endpoints							
Primary								
To establish the dose-response relationship for antiviral activity of 3 doses of JNJ-3989+NA and to evaluate the efficacy of combination regimens of JNJ-3989+NA (with and without JNJ-6379) and of JNJ-6379+NA.	Proportion of participants meeting the NA treatment completion criteria at Week 48 (see Individual Participant NA Treatment Completion Criteria).							
Secondary								

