With the low rate of functional cure with current treatments, and persistently high global prevalence of HBV-associated mortality,^{7,35} there is a medical need for more effective finite treatment options that lead to sustained HBsAg seroclearance ("functional cure"). In order to achieve an effective finite treatment, combination of therapies with different mechanisms of action, as is standard of care for other chronic viral infections like HCV and HIV, is deemed required.

JNJ-73763989 and JNJ-56136379

JNJ-73763989 (JNJ-3989) is a liver-targeted antiviral therapeutic for subcutaneous injection designed to treat chronic HBV infection via a ribonucleic acid interference (RNAi) mechanism. Engagement of the cellular RNAi machinery by JNJ-3989 results in specific cleavage of HBV ribonucleic acid (RNA) transcripts, thereby reducing the levels of HBV proteins and the pgRNA, the precursor of viral relaxed circular DNA. The RNAi triggers in JNJ-3989 injection are designed to target all HBV RNA transcripts derived from covalently closed circular DNA (cccDNA), as well as transcripts derived from integrated viral DNA. The latter has been suggested to be a significant source of HBsAg in HBeAg-negative patients or patients on long-term treatment with NAs, the current standard of care.³⁷

JNJ-56136379 (JNJ-6379) is an orally administered capsid assembly modulator (CAM) that is being developed for the treatment of chronic HBV infection. JNJ-6379 binds to HBc and interferes with the viral capsid assembly process, thereby preventing the polymerase-bound pgRNA encapsidation. This results in the formation of HBV capsids, devoid of HBV DNA or RNA (non-functional capsids), and ultimately in the inhibition of HBV replication. In addition, JNJ-6379 also acts at an early stage of the viral life cycle by inhibiting the de-novo formation of cccDNA potentially by interfering with the capsid disassembly process.

For the most comprehensive nonclinical and clinical information regarding JNJ-3989 and JNJ-6379, refer to the latest version of the Investigator's Brochure (IB) and Addenda. ^{13,14,15}

The term "study intervention" throughout the protocol, refers to JNJ-3989 or placebo, JNJ-6379 or placebo, and NA.

The term "sponsor" used throughout this document refers to the entities listed in the Contact Information page(s), which will be provided as a separate document.

The term "participant" throughout the protocol refers to the common term "subject".

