Peripheral blood mononuclear cell (PBMC) samples for immune analyses will be collected at selected sites at the time points indicated in the Schedule of Activities (see Section 8.7)

A pharmacogenomic blood sample will be collected from participants who consent separately to this component of the study (see Section 8.8).

The study includes collection of blood samples for exploratory analysis of viral markers (see Section 8.1) and host blood biomarkers at the host RNA, protein, and cell level (see Section 8.9).

If a participant prematurely discontinues investigational intervention (before Week 48), the participant will enter the follow-up phase and complete the follow-up schedule as per the Schedule of Activities, unless the participant withdraws consent. In this case, NA treatment may be continued or, in consultation with the sponsor, discontinued based on investigator judgement or completed based on the NA treatment completion criteria (see Section 6.6).

If a participant withdraws consent before completing the study, the reason for withdrawal is to be documented in the case report form (CRF) and in the source documents. Participants who withdraw consent will be offered an optional safety follow-up visit.

An IDMC will be commissioned for this study. In addition, an IFLEP will be appointed (see Section 9.5).

A diagram of the study design is provided in Section 1.2, Schema.

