6.5. Concomitant Therapy

Prestudy therapies administered up to 30 days before the start of screening must be recorded at screening. If applicable, the participant's last anti-HBV treatment prior to screening must also be recorded.

Concomitant therapies must be recorded throughout the study, from signing of the ICF up to the last study visit. Concomitant therapies should also be recorded beyond the last study visit only in conjunction with new or worsening (S)AEs.

All therapies (prescription or over-the-counter medications, including vaccines, vitamins, herbal supplements; non-pharmacologic therapies such as electrical stimulation, acupuncture, special diets, exercise regimens) different from the study intervention must be recorded in the CRF. Recorded information will include a description of the type of therapy, duration of use, dosing regimen, route of administration, and its indication. Modification of an effective pre-existing therapy should not be made for the explicit purpose of entering a participant into the study.

An overview of disallowed medication is provided in Table 4.

Table 4: Disallowed Medication

Disallowed at any time prior to screening until end of follow-up:

• Any CAM and oligonucleotide-based treatment (eg, siRNA and antisense oligonucleotides), other than the study intervention taken in the context of this study.

Disallowed from 6 months prior to screening until end of follow-up:

• Any investigational agent, investigational vaccine, invasive investigational medical device, or investigational biological product (other than the study intervention taken in the context of this study).

Disallowed from 6 months prior to baseline until end of follow-up:

- For participants currently not being treated: Any anti-HBV drug (including vaccines) other than the study intervention taken in the context of this study.
 Note: Prior hepatic treatment with herbal or nutritional products is allowed but should be stopped at screening.
- Any systemically (eg, intravenously, intramuscularly, orally, subcutaneously) administered medication that directly or indirectly interferes with immune responses (eg, cyclosporine, interleukins, IFN, systemic corticosteroids exceeding 5 mg of prednisolone equivalent/day).

Disallowed from 1 month prior to screening until end of follow-up:

- Moderate and potent inhibitors of CYP3A4 (eg, azole anti-fungals, macrolide antibiotics, diltiazem, verapamil).

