7. DISCONTINUATION OF STUDY INTERVENTION AND PARTICIPANT DISCONTINUATION/WITHDRAWAL

7.1. Discontinuation of Study Intervention

A participant's investigational intervention **must** be discontinued if any of the criteria listed below apply. In those cases, NA treatment may be continued or, in consultation with the sponsor, discontinued based on investigator judgement or completed based on the NA treatment completion criteria (see Section 6.6).

- The investigator believes that for safety or tolerability reasons (eg, AE) it is in the best interest of the participant to discontinue investigational intervention.
- The participant becomes pregnant.
- The participant has a ≥grade 3 rash (see Section 10.5, Appendix 5, Rash Management) or allergic reaction (see Section 8.3.6.3).
- The participant has signs of hepatic decompensation (ie, clinical evidence of ascites, bleeding varices, or hepatic encephalopathy).
- The participant has a confirmed ≥grade 3 estimated glomerular filtration rate (eGFR) abnormality and a drop from baseline of >10 mL/min/1.73 m², considered at least possibly related to JNJ-3989 or JNJ-6379. Change of NA treatment should be considered anytime, according to the prescribing information. (see Section 8.3.6.4).
- The participant has a confirmed QTcF prolongation (defined as a QTcF value of >500 ms, or an increase from baseline of >60 ms) at any given time point.

- The participant requires ≥7 days of treatment with any of the disallowed medications listed in Section 6.5 and does not intend to discontinue treatment with the disallowed medication.
- The participant has confirmed HBV virologic breakthrough (ie, confirmed on-treatment HBV DNA increase by >1 log₁₀ IU/mL from nadir or confirmed on-treatment HBV DNA level >200 IU/mL in participants who had HBV DNA level <LLOQ of the HBV DNA assay). In case of virologic breakthrough, changing the NA should be considered in consultation with the sponsor.
- The participant has ALT/AST elevations, as described in Section 8.3.6.1, Interventionemergent ALT/AST Elevations.

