ICS intracellular cytokine staining

IDMC Independent Data Monitoring Committee

IEC Independent Ethics Committee
IFLEP Independent Flare Expert Panel

 $\begin{array}{ll} \text{IFN} & \text{interferon} \\ \text{IFN-}\gamma & \text{gamma interferon} \\ \text{IgM} & \text{immunoglobulin M} \end{array}$

IL interleukin

INR International Normalized Ratio
IRB Institutional Review Board
ISR injection site reaction

ITT Intent-to-treat

IU/mL International Units Per Milliliter IWRS interactive web response system

LLN lower limit of normal LLOQ lower limit of quantification

MCP-Mod Multiple Comparison Procedure-Modeling

MCT Multiple Contrast Test
MH Mantel-Haenszel
MoA mode of action

MRI magnetic resonance imaging

NA nucleos(t)ide analog

NOAEL no observed adverse effect level

PD pharmacodynamic(s)

PGIC Patient Global Impression of Change

PK pharmacokinetic(s)

PBMC peripheral blood mononuclear cell pgRNA pre-genomic ribonucleic acid

PI prediction interval

PQC Product Quality Complaint PRO patient-reported outcome

qd once daily

QTcF QT interval corrected for heart rate according to Fridericia

RBC red blood cell RNA ribonucleic acid

 $\begin{array}{lll} RNAi & ribonucleic \ acid \ interference \\ SAE & serious \ adverse \ event \\ SAP & Statistical \ Analysis \ Plan \\ SBP & systolic \ blood \ pressure \\ SD & standard \ deviation \\ SigE_{max} & sigmoid \ E_{max} \end{array}$

siRNA small interfering RNA

SUSAR suspected unexpected serious adverse reaction

 $t_{1/2 term}$ terminal half-life

t_{max} time to reach the maximum plasma concentration TAF tenofovir alafenamide

TDF tenofovir disoproxil fumarate TNF tumor necrosis factor

ULN upper limit of normal US United States WBC white blood cell

Definitions of Terms

Study intervention JNJ-73763989 or placebo, JNJ-56136379 or placebo, and NA (either ETV, TDF, or TAF)

Functional cure HBsAg seroclearance 24 weeks after end of treatment

HBsAg or HBeAg

seroclearance

HBsAg or HBeAg negativity, respectively, based on the assay used

HBsAg or HBeAg seroconversion

HBsAg or HBeAg negativity and anti-HBs or anti-HBe antibody positivity, respectively

Virologic

breakthrough

Confirmed on-treatment HBV DNA increase by >1 log₁₀ IU/mL from nadir or confirmed on-treatment HBV DNA level >200 IU/mL in participants who had HBV DNA level

<LLOQ of the HBV DNA assay

ALT/AST nadir Lowest ALT/AST value during study participation

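### Read literally, the rash rule in Protocol Section 8.3.6.2 orders a permanent stop of the nucleos(t)ide analog, which the protocol's neighboring rules leave optional

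*Protocol*

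**What the plan says.** The rash section (Protocol 8.3.6.2) contains one stopping rule of its own: "If systemic corticosteroids exceeding 5 mg of prednisolone equivalent/day are required for treatment of rash, the study intervention needs to be permanently discontinued". It sets no rash grade, no duration of steroid use and no exception for the NA.

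The term is defined three times, each time with the NA inside it. The Synopsis (1.1) has "Study intervention refers to JNJ-3989 or placebo, JNJ-6379 or placebo, and NA". The Introduction (Section 2) says the term, throughout the protocol, "refers to JNJ-3989 or placebo, JNJ-6379 or placebo, and NA". Appendix 1 (10.1) lists "JNJ-73763989 or placebo, JNJ-56136379 or placebo, and NA (either ETV, TDF, or TAF)".

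Section 7.1 is the main stopping section. Its list of triggers requires the investigational intervention to stop and then treats the NA separately: "In those cases, NA treatment may be continued or, in consultation with the sponsor, discontinued based on investigator judgement", or completed on the Section 6.6 criteria. One trigger is rash of grade 3 or higher. Another is a need for 7 or more "days of treatment with any of the disallowed medications listed in Section 6.5" with no intention of stopping the drug. Table 4 in Section 6.5 names, among the disallowed drugs, "systemic corticosteroids exceeding 5 mg of prednisolone equivalent/day".

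Section 4.1 gives the general position after any premature stop of investigational intervention: "In this case, NA treatment may be continued or, in consultation with the sponsor, discontinued based on investigator judgement or completed" on the completion criteria. Section 6.6 also lets the NA continue, and ties an NA stop to those criteria. Table 9 (Appendix 5) requires a permanent stop of JNJ-3989 and JNJ-6379 for Grade 3 and Grade 4 rash. It makes an NA stop a matter of investigator judgement with the sponsor.

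**The concern.** The same participant can come under a rule that, by its defined term, orders a permanent NA stop and under others that leave the NA to judgement or to the completion criteria. A site that follows 8.3.6.2 to the letter would withdraw the NA from someone who need not have met the Section 6.6 criteria.

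The protocol gives its own reasons for caution here. Section 2.3.2.2 names hepatitis B flare as a risk of stopping the NA. Section 4.2 explains that the completion criteria are there so that only participants with some prospect of a lasting off-treatment response stop everything. What is at stake is participant safety and a clear instruction to sites. Sample size, alpha, endpoint definitions and planned analyses are untouched.

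**Working it through.** No arithmetic on trial data applies, so the check sets the rules side by side.

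| Place | When it applies | Investigational products | NA |
|---|---|---|---|
| 8.3.6.2 | Rash needing systemic steroids above 5 mg/day; no grade or duration condition | Permanent stop | Permanent stop, by the defined term |
| 7.1, rash trigger | Rash of grade 3 or higher | Must stop | Optional |
| 7.1, medication trigger, with Table 4 | 7 or more days of a disallowed drug and no intent to stop it; steroids above 5 mg/day are listed | Must stop | Optional |
| 7.1, safety trigger | Investigator judges that stopping is best for safety or tolerability, for example because of an adverse event | Must stop | Optional |
| 4.1 | Any premature stop of investigational intervention | Already stopped | May continue; stop on judgement or on the completion criteria |
| 6.6 | Same | Already stopped | May continue; stop on the completion criteria |
| Table 9, Grades 3 and 4 | Rash of that grade | Permanent stop | Optional |

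**Step 1: is the dose cut-off the same?** Yes. It is above 5 mg prednisolone equivalent per day in both 8.3.6.2 and Table 4.

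**Step 2: are the triggers the same?** No. The medication trigger in 7.1 adds two conditions that 8.3.6.2 lacks: at least 7 days of treatment and no intent to discontinue. That gives three cases:

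- Grade 3 or 4 rash given steroids: 8.3.6.2, the 7.1 rash trigger and Table 9 all apply. Only 8.3.6.2 requires the NA to stop.
- Grade 1 or 2 rash, steroids for 7 or more days with no intent to stop: 8.3.6.2 and the 7.1 medication trigger apply. Again only 8.3.6.2 requires it.
- Grade 1 or 2 rash, short steroid course: among the specific rash and medication rules, only 8.3.6.2 applies. The general safety trigger in 7.1 stays open to the investigator, and 4.1 and 6.6 still describe the NA as something that may continue.

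**Step 3: how many 7.1 triggers can overlap?** The list holds 9: investigator safety judgement; pregnancy; rash or allergic reaction of grade 3 or higher; hepatic decompensation; eGFR; QTcF; disallowed medication; virologic breakthrough; ALT/AST elevation. At least 3 can cover a rash treated with steroids (safety judgement, grade 3 or higher rash, disallowed medication). None of the 3 requires an NA stop.

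**Step 4: does the literal reading make clinical sense?** Not obviously. It would be stricter about the NA for a mild rash given a few days of steroids than Table 9 is for Grade 4 rash, which includes Stevens-Johnson syndrome. That points to a slip in the term, not a deliberate rule.

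**The case against.** The best defense is that no careful reader would take the term literally.

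- Section 7.1 carries the broad term in its title while its trigger list stops only the investigational intervention. Its closing paragraph, like footnote c to the treatment-phase schedule, sends participants who discontinue study intervention early into follow-up. Footnote e to the follow-up schedule still dispenses NA there to those who have not met the completion criteria. The term is also loose in Section 4.2.1 and the COVID-19 Appendix.
- Section 8.3.6.2 itself points to Table 9, where a site would find the NA handled separately for Grades 3 and 4.
- Section 7.1, Section 4.1 and Table 9 permit an NA stop. The conflict is therefore between a mandatory and a discretionary rule, not between opposite orders.
- Anyone who did stop the NA would enter scheduled follow-up, and Section 6.7 gives criteria for re-starting it.

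Most of this stands, and it limits how much weight the point can carry. It does not remove the mismatch. Table 9 has no NA clause for Grades 1 and 2, which is where 8.3.6.2 is most likely to be the only specific rule. Section 6.7 is introduced for participants who met the completion criteria, and a permanent stop sits awkwardly with re-start rules.

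A reader might infer three stronger things. One is that 8.3.6.2 and 7.1 give different orders for one identical situation; the added duration and intent conditions in 7.1 rule that out. Another is that a tally of stopping rules shows 8.3.6.2 to be a lone outlier. The broad term appears in other stopping instructions, and Section 8.3.6.5 only asks that discontinuation be considered, so such a tally proves little. The third is that the sponsor intended to withdraw the NA for steroid-treated rash, or that the study's results are at risk. Nothing in either document supports that.

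**Conclusion.** The inconsistency is real. By the protocol's own definition, 8.3.6.2 makes a permanent NA stop mandatory, while 7.1, 4.1, 6.6 and Table 9 (Grades 3 and 4) never require one. It merits a minor safety-wording correction and is not a condition for proceeding with the trial.

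This rests on reading the defined term as written. The documents do not say how many participants would need such steroids for rash; the assumption here is that they are few. No endpoint definition or analysis changes on either reading. The reason to act is that this is a mandatory safety instruction, and its literal form bypasses the criteria the protocol set for stopping the NA.

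**What to change.** In Section 8.3.6.2, change what must permanently stop from the study intervention to the investigational intervention (JNJ-3989/placebo and JNJ-6379/placebo). Follow it with the NA clause already used in Section 7.1, "In those cases, NA treatment may be continued or, in consultation with the sponsor, discontinued based on investigator judgement", including its ending that the NA may be completed on the completion criteria. Cross-refer to Section 7.1 and Table 9. Leave the steroid trigger as it is.

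There is a precedent: Appendix 13 records that Amendment 2 made the same change of term in Section 8.3.5 (Pregnancy) and logged it as a correction. The cost is one term and one existing clause, in the next amendment or a clarification letter to sites. It adds no visits, tests or data.
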